#### 4.4 Schedule of Events

Evaluation	Preop	Intraop	Inpatient	D1	D2	D3	D4	D6	D8	D10	D12	W1-2	W4-6	D30	D90
Demographics	X														
Medical History / Comorbidities	X														
Surgical Details		X													
Discharge (LOS, disposition)			X												
Track Readmission / Reoperation													X	X	
Track ED visits, office visits													X	X	
Track calls and on-call pages													X	X	
Adverse Events	X	X											X	X	
Postop Check-in Check-up				X	X	X	X	X	X	X	X				
Recovery Goals												X	X		
HOOS Jr / KOOS Jr	X													X	
Promise 10	X													X	
Patient Satisfaction (VAS and PPE-15)														X	X
Provider Satisfaction (5-point Likert)															X

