## **1. Project Summary**

JointCOACH is a web-based communication platform that enables joint replacement patients to communicate with their care team via computer or smartphone throughout their episode of care, from the time that surgery is scheduled until at least 90 days postoperatively. Patients will receive the following information at key intervals: 1) instructions about how to prepare for surgery, 2) information about the procedure, 3) information about medications and pain control, 4) information about postoperative recovery and rehabilitation. In addition, several surveys will be distributed using JointCOACH to keep patients involved in their own recovery and to keep the surgical team informed of their progress. The proposed research will help determine if JointCOACH can improve patient satisfaction and clinical outcomes.

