## **2. Introduction and Background**

Health systems invest significant resources to improve quality and reduce costs. However, this process is typically driven by hospital administration and staff. Recently, studies have shown that when patients are engaged, they take more responsibility for their own health and preventative care. Additionally, these patients are more satisfied with their healthcare experiences and have lower rates of healthcare utilization . Physicians are in the best position to promote patient engagement since they have direct relationships with their own patients. However, physicians need frictionless tools with minimal implementation barriers in order to create and maintain this relationship in the follow up period.

Patient engagement has been referred to as the next blockbuster “drug”, and increasing evidence demonstrates that highly engaged patients not only enjoy improved outcomes, but have fewer complications, undergo fewer readmissions, and have lower total costs of care . While these engagement-related outcomes have been shown in several other specialties, relatively little has been done to explore this relationship in orthopedics. The opportunity to demonstrate the

impact of engagement on outcomes in the orthopedic space is highlighted by the estimated \$1.5B of medical expenses occurring nationally due to potentially preventable readmissions following orthopedic surgeries alone.

Stryker Performance Solutions JointCOACH™ and the Cleveland Clinic are interested in collaborating on a clinical pilot study to demonstrate that high patient engagement leads to enhanced preoperative preparation potentially reducing length of stay (LOS), readmissions and reoperations, increasing discharge disposition to home rather than another facility, reducing the need for in-person follow up, and increasing patient (and provider) satisfaction after elective primary hip and knee arthroplasty (THA and TKA). These improvements can translate to higher financial savings through the episode of care especially in light of the alternative payment models.

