### **3. Specific Aims**

Currently in use by orthopedic groups around the country, JointCOACH improves perioperative outcomes after THA and TKA and mitigates risk by: 1) enhancing patient engagement with providers, 2) allowing patients to play an integral role in patient-reported outcomes, 3) generating and relaying actionable pre- and postoperative reporting directly to the clinical team, and 4) detecting impending postoperative complications early, enabling timely intervention and preventing avoidable complications and readmissions. The specific aims of this proposal are to:

1. Measure patient satisfaction with and without use of JointCOACH as a tool for patient engagement
2. Understand the degree to which high postoperative engagement can reduce the amount of healthcare resource utilization by answering the following questions:

- a. Will the use of JointCOACH decrease the number of potentially avoidable healthcare utilization encounters such as Emergency Department (ED) and hospital visits (i.e. readmissions and reoperations)?
  - b. Does utilizing JointCOACH improve clinical workflow by minimizing telephone calls and thereby offloading support staff, allowing them to be more efficient?
  - c. Does utilizing JointCOACH reduce the volume of on-call pages by addressing patient questions up front, alleviating concerns, and providing them with the information they need when they need it?
  - d. Does utilizing JointCOACH allow the practice to identify patients whose in-person follow-up needs are minimal?
3. Measure additional potential benefits including shorter length of hospital stay, discharge disposition to home rather than a facility and decreased 90 day readmissions and reoperations by answering the following:
  - a. Does utilizing JointCOACH lead to early detection of adverse signs/symptoms that develop between clinical encounters and result in reduced readmissions and reoperations?
4. Evaluate the financial impact of JointCOACH in the episode of care (% difference in Charges between JointCOACH and standard of care groups)

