## 6. Appendix

### 6.1 Study Metrics

Metric	Justification
Patient Reported satisfaction – VAS and PPE-15	-Substantial opportunity for the Cleveland Clinic to differentiate itself among health systems and enhance revenue associated with patient satisfaction measures
Patient utilization and compliance	- Substantial opportunity for national exposure as related to national directives to drive patient engagement (See NCQA's Leadership Series: Focus on Patient Engagement at http://www.qualityprofiles.org/leadership_series/patient_engagement/index_patient_engagement.asp )
Physician and staff satisfaction	- Opportunity to demonstrate clinical adoption rates and low barriers to implementation.
Total 90 day post-operative cost from index date+1 (same day) or from index date + LOS (inpatient)*  *Claims submitted within 90 days must be limited to ICD-10 listed below (or if hospitalization due to ICD-10 below) in order to exclude unrelated claims.	Joint Coach templates should be able to either prevent the complication, or through early detection at the clinic level, reduce expense through minimized emergency room visits and readmissions.
30 day post-op hospitalization rate (this is a readmission if initially an inpatient procedure, or an admission if initially an outpatient procedure)*  *Must be associated with ICD-10s listed below in order to exclude unrelated readmissions.	
30-day ED Visit Rate*  *Must be associated with ICD-10s listed below in order to exclude unrelated ED visits.	
Number of follow up visits within 90 days	Demonstration to physicians and practices the potential to improve throughput and workflow efficiency by minimizing the number of follow up visits required.

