Potentially preventable readmissions and complications identified using JointCOACH	Potentially preventable admissions, events, ED visits. Using an approach similar to 3M's Potentially Preventable Events grouping software, we will examine all events (ED visits, admissions, complications) for relation to index event, and compare this rate to prior year. Data may be supplemented by Physician survey. http://solutions.3m.com/wps/portal/3M/en_US/Health-Information-Systems/HIS/Products-and-Services/Products-List-A-Z/PPR-and-PPC-Grouping-Software/

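### The complication metric depends on JointCOACH and on a prior-year comparator, and no common event source is set for the two randomized arms

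*Combined protocol and SAP*

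**What the plan says.** Section 4.4 has one schedule for the whole trial. Its "Postop Check-in Check-up" row is marked at D1, D2, D3, D4, D6, D8, D10 and D12, and Recovery Goals follow at W1-2 and W4-6. No row says which arm it covers. The Adverse Events row is marked at Preop, Intraop and two later points (W4-6 and D30 as the table reads), with nothing from D1 to D12.

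Section 1 states that "several surveys will be distributed using JointCOACH to keep patients involved in their own recovery and to keep the surgical team informed of their progress". Section 3 gives as one of the tool's functions "detecting impending postoperative complications early, enabling timely intervention and preventing avoidable complications and readmissions". Aim 3a opens with "Does utilizing JointCOACH lead to early detection of adverse signs/symptoms that develop between clinical encounters" and goes on to ask whether readmissions and reoperations fall as a result. Section 2 names "reducing the need for in-person follow up" among the hoped-for benefits, and section 6.1 likewise looks for fewer follow-up visits over 90 days.

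Section 6.1 also lists the metric "Potentially preventable readmissions and complications identified using JointCOACH". The text beside it says that all events will be reviewed for a link to the index procedure, that the rate will be set against the prior year, and that a physician survey may add data. The 30-day hospitalization and ED metrics in 6.1 are tied to the diagnosis codes in 6.2.

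Section 4.1 lists ED visits, readmissions and reoperations within 90 days, but not adverse events. Section 4.5 specifies one analysis, the t-test on PPE-15.

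**The concern.** JointCOACH is both the treatment under test and, by the protocol's own account, a means of finding complications. An event count that relies on the tool measures how hard one looked as well as how often events occurred. A prior-year cohort has no equivalent unless the tool was already in use at these sites, which the plan does not say. The randomized control arm, which is the natural comparator, is not used for this metric.

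The same issue reaches any table of complications or adverse events by arm. Frequent check-ins in one arm would raise the share of events that become known. Fewer office visits in that arm would lower it. Without a source common to both arms, an observed difference cannot be divided into true effect and detection. ED visits and readmissions are less exposed, but those that occur outside the health system could become known through the platform in one arm only. What is at stake is the reading of the secondary aims on utilization and early detection (Aims 2a and 3a).

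**Working it through.** **No plan figure to reproduce.** The documents give no complication or adverse event rate and no capture probability. The 153 per group in 4.3 concerns PPE-15 only. The figure of under 4% in 6.3 is a success threshold for 30-day hospitalization, not an expected complication rate.

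**Step 1: contacts in the early period (4.4).** Check-in marks from D1 to D12: 8. Adverse Events marks from D1 to D12: 0. The two later Adverse Events marks may sit one column off in the text as read, because the ED and readmission rows also end at D30 while 4.1 counts those outcomes to 90 days. On any plausible reading they still fall after the check-in block.

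**Step 2: which arm gets the check-ins.** Section 4.4 does not say. Section 1 routes surveys through JointCOACH, so the natural reading is the JointCOACH arm only, and detection effort then differs by arm. If both arms receive them, control patients receive part of the intervention. Either way the schedule needs an arm label. The check-in's content is not given; that it looks for complications is inferred from the functions listed in section 3.

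**Step 3: the 6.1 metric.** The title restricts the count to events found with the tool. The adjacent text speaks of all events. The comparator is the prior year. If the title governs, numerator and comparator are collected by different means. If the text governs, the title is wrong and the randomized control is still passed over.

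**Step 4: direction and size, on assumed inputs.** Let p be the true risk, equal in both arms, and s0 and s1 the shares of events captured in the standard-of-care and JointCOACH arms. Then

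- observed difference = p × (s1 − s0)
- observed ratio = s1 / s0

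| True risk p | s0 = 80%, s1 = 90% | s0 = 70%, s1 = 95% | s0 = 90%, s1 = 70% |
|---|---|---|---|
| 5% | 4.0% v 4.5%: +0.5 | 3.5% v 4.75%: +1.25 | 4.5% v 3.5%: -1.0 |
| 10% | 8.0% v 9.0%: +1.0 | 7.0% v 9.5%: +2.5 | 9.0% v 7.0%: -2.0 |
| 20% | 16.0% v 18.0%: +2.0 | 14.0% v 19.0%: +5.0 | 18.0% v 14.0%: -4.0 |
| Ratio | 1.12 | 1.36 | 0.78 |

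Entries are standard of care v JointCOACH, with the difference in percentage points. The first two scenarios let the check-ins dominate; the third lets the lost visits dominate. The sign depends only on whether s1 exceeds s0, and the documents do not settle that. At 200 per arm, the 10% row of the middle scenario is 14 v 19 recorded events with no true difference.

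**The case against.** The strongest reply is that the plan contains no between-arm safety test. Adverse events are not in the 4.1 outcome list, and 4.5 covers PPE-15 alone. A reader might infer that the trial's safety comparison is already biased. The documents do not support that: no such comparison is described, and the Adverse Events row makes no distinction between arms.

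A second reply concerns Aim 3a, whose endpoints are readmissions and reoperations. These are hard events, and the 6.2 code rule for hospitalizations and ED visits does not depend on arm. If earlier detection lowers readmissions, that is the intended effect and not bias. This stands.

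Third, the schedule marks do not prove that early adverse events go uncollected in the control arm. They may be points at which events are gathered cumulatively, and the contacts included in standard care are not described. A reader might also expect an excess of recorded events with JointCOACH; the third scenario above shows that the opposite is equally possible.

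Fourth, reports from the tool reach the clinical team, so an event prompted by a check-in may be charted, and a chart review would then carry some of the same differential detection. This also stands, as a limit on what the remedy can achieve.

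What remains is the 6.1 metric, whose title depends on the tool and whose comparator is historical, and the absence of a stated common source for events that two of the aims and the 4.1 outcome list will lead readers to compare by arm.

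**Conclusion.** The concern holds in a limited form. The 6.1 complication metric, as titled, depends on the tool and is not comparable with the prior year. Any between-arm comparison of complications or adverse events, and to a lesser degree of ED visits and readmissions outside the system, is open to ascertainment bias of unknown direction. This rests on two inferences: that the check-ins go only to the JointCOACH arm, and that they ask about symptoms or complications.

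The size cannot be derived from the documents. The spurious differences in the table show only that a few points either way would arise under assumed inputs; they are not estimates for this trial. The primary PPE-15 analysis is untouched. The change is worth making before events are tabulated by arm, because early events captured unequally cannot be reliably recovered later.

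**What to change.** 1. **Section 6.1.** Redefine the complication metric as events counted by one rule, the ICD-10 list in 6.2, in both randomized arms. Make the control arm the main comparator; the prior year can stay as background.
2. **Section 4.4.** State which arm each row applies to. Add the same short event questions for all patients (ED visit, hospital stay or complication anywhere, with dates) at the D30 and D90 contacts where PPE-15 is already collected. Add one chart review from surgery to D90, done by the same rule in both arms. The review also covers patients who do not answer: the sample size allows for (200 − 153)/200 = 23.5% withdrawals and non-responders.
3. **Section 4.5.** Tabulate events known only from a JointCOACH check-in separately and keep them out of the between-arm comparison. Say whether adverse events will be compared between arms.

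The cost is a few questions at existing contacts, one chart review and some wording. Mild events seen only at check-in leave the comparison, though they are still reported. Chart review may still include some events prompted by check-ins, and the plan should state this as a limitation. Nothing here alters how check-in answers are used in care.

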#### **4.5 Data Analysis Plan**

The difference in percent of respondents indicating a problem on the PPE-15 between treatment and control groups will be calculated as [percent of standard of care respondents reporting a problem, averaged across all PPE-15 domains] – [percent of JointCOACH respondents reporting a problem, averaged across all PPE-15 domains], such that a positive difference indicates that the JointCOACH group was more satisfied than the standard of care group, while a negative value indicates the opposite. A superiority hypothesis test using the two-independent sample t-test will be used to statistically evaluate the difference in the average satisfaction between groups.

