#### **4.3 Sample Size Calculation**

We will enroll 400 patients (200 in each group). This sample size was estimated using patient reported satisfaction based on the PPE-15 questionnaire as the primary endpoint. Currently, it is not known what will be a clinically relevant difference so we conservatively estimated that a 10% difference in patient satisfaction (difference in % of respondents indicating a problem on the PPE-15 between treatment and control groups) would be relevant. Based on data published in a study by Jenkinson et al, we used a mean of 24.7% ( $\pm$  7.7) for the percent of respondents across all PPE-15 domains that identified a problem with their experience. Setting alpha equal to 0.05 and power equal to 80%, we determined that we will need 153 patients in each group. However, we will enroll 200 patients in each group to account for withdrawals and non-responders.

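### The primary PPE-15 comparison is computed among respondents only, and neither the sample-size headroom nor an unstated survey route protects it from response bias that differs by arm

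*Combined protocol and SAP*

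**What the plan says.** Section 4.3 takes "patient reported satisfaction based on the PPE-15 questionnaire as the primary endpoint". It calculates 153 patients per group and enrols 200 per group "to account for withdrawals and non-responders".

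Section 4.5 defines the primary difference as control minus JointCOACH. Each term is an average over PPE-15 domains among those who responded; the second term is the "percent of JointCOACH respondents reporting a problem". The test is a two-sample t-test for superiority.

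No section states an analysis set, a rule for missing forms or items, a sensitivity analysis, or a comparison of responders with non-responders.

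On survey delivery, Section 1 says that "several surveys will be distributed using JointCOACH to keep patients involved in their own recovery" and to keep the surgical team informed. The documents do not say whether the PPE-15 is one of these surveys, or by what route either arm receives it. Section 4.4 schedules the PPE-15 and the VAS at two postoperative times (D30 and D90 as the extracted table reads), without naming the primary one.

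**The concern.** Randomisation makes the two arms comparable as assigned. It does not make the people who return a questionnaire comparable. Enrolling extra patients restores the number of forms, but leaves open who returned them.

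The question matters more here than in most trials because the intervention is itself a tool for engagement and surveys. Section 2 argues that engaged patients are more satisfied. Section 6.3 counts engagement as successful when at least 70% of users reach a set level, so up to 30% may fall short. If engagement also influences who answers the PPE-15, missingness in the JointCOACH arm is linked to the endpoint through a mechanism that the control arm lacks.

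At stake is the primary conclusion. The difference on which the trial was sized is small, so a moderate response bias can matter in either direction.

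**Working it through.** **1. The plan's own figure.** Inputs from Section 4.3: control mean 24.7%, SD 7.7, alpha 0.05, power 80%, and a target given as "we conservatively estimated that a 10% difference in patient satisfaction". Read as relative, the target is 0.10 × 24.7 = 2.47 points. Then

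n per arm = 2 × [7.7 × (1.960 + 0.842) / 2.47]² = 152.6, rounded up to 153.

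This reproduces the stated figure with a two-sided test. A one-sided test gives 121. Read as 10 absolute points, the same formula gives 10 per arm. So 2.47 points is the target on which the size rests, although the wording can be read as absolute.

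**2. Headroom.** 200 − 153 = 47, and 47/200 = 23.5% per arm. This is inferred. It covers withdrawals and non-response together, and is neither a stated cap nor an expected rate.

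**3. Bias formula.** Let m be the missing fraction in an arm and g the non-responder mean minus the responder mean. The responder mean differs from the full-arm mean by −m × g. For control (C) minus JointCOACH (J),

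bias = m_J × g_J − m_C × g_C.

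If g = 0 in both arms, the bias is zero at any response rates. If m and g are the same in both arms, the bias cancels. Bias needs a non-zero g and a difference between arms in m or g.

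**4. Size with 23.5% missing in each arm and a gap in one arm only.** The gaps are assumptions; the documents give no response data. The SE of the difference at 153 per arm is 7.7 × √(2/153) = 0.88 points, so the two-sided significance threshold is 1.96 × 0.88 = 1.73 points.

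| Gap in one arm | Bias = 0.235 × gap | False-positive rate, no true effect | Power for a true 2.47 if bias opposes it |
|---|---|---|---|
| 0 | 0 | 5% | 80% |
| 3.85 (half SD) | 0.90 | about 18% | about 43% |
| 7.7 (one SD) | 1.81 | about 54% | about 12% |

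The direction depends on the arm. If only JointCOACH non-responders are less satisfied, a false benefit appears. If only control non-responders are, a real benefit is hidden.

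**5. Gap needed for the whole target.**
- One arm only: 2.47 / 0.235 = 10.5 points, or 10.5 / 7.7 = 1.37 SD.
- Opposite directions in the two arms: 2.47 / (2 × 0.235) = 5.3 points each.
- Same gap in both arms with unequal response (assumed 33.5% and 13.5% missing): 2.47 / 0.20 = 12.4 points. If JointCOACH responds better and non-responders are less satisfied, this bias runs against JointCOACH.
- If the target is 10 absolute points, one arm only: 10 / 0.235 = 42.6 points.

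**6. What depends on the SD and the target.** With no true effect, bias/SE for a half-SD gap is 0.235 × 0.5 / √(2/153) = 1.03, whatever the SD or target. The false-positive rate of about 18% therefore stands on either reading of the 10%. The loss of power applies to the 2.47-point reading.

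**The case against.** - **The PPE-15 is sent through JointCOACH.** A reader might infer this from Section 1. The documents do not say so. The sentence fits the check-in and recovery-goal surveys in Section 4.4 at least as well. Only an unspecified collection route can be shown, so a claim that response is likely to differ by arm has no figure behind it.
- **Unequal response alone distorts the result.** It does not; step 3 shows that response must also be related to satisfaction.
- **The plan tolerates nearly a quarter non-response.** The 23.5% is recruitment headroom inferred from two numbers, and it includes withdrawals.
- **Response bias can readily create or hide the whole effect.** On the 2.47-point target this needs a one-arm gap of 1.37 planned SDs; on an absolute 10-point target the gap is extreme. The SD of 7.7 is described as applying across domains. If the patient-level SD is larger (assumed 100 × √(0.247 × 0.753 / 15) = 11.1 for independent items), 10.5 points is 0.94 SD and easier to reach.
- **Respondents may be ordinary questionnaire language.** Section 4.5 does not expressly rule out imputation. Even so, carrying out the section as written gives a respondents-only analysis, and nothing elsewhere provides another.
- **There is some mitigation.** Section 4.2 requires internet or mobile access with a valid e-mail address and excludes abandoned addresses, in both arms. This reduces differences caused by access, but not those caused by engagement or satisfaction.

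**Conclusion.** The point holds in a limited form. As written, the primary analysis compares respondents, the added enrolment guards power only, and the route of PPE-15 collection is open in a trial whose intervention delivers surveys in one arm. The comparison is biased if response relates to satisfaction and its rate or selection differs by arm.

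Under the stated assumptions the plausible damage is moderate to serious: 0.90 points for a half-SD gap in one arm and 1.81 points for one SD, against a 2.47-point target. Loss or creation of the entire target is the far end of the range. The documents do not show that differential response will occur; they show that the plan neither prevents it nor would reveal its effect. The matter should be corrected, but it does not invalidate the design.

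**What to change.** 1. In Section 4.5, make the primary set all randomised patients by assigned arm. Use multiple imputation by arm, or a repeated-measures model, drawing on the other visit's PPE-15, the VAS, preoperative scores, procedure, site, and readmission and ED events. All of these are already scheduled or recorded. Name the primary visit, since the other visit's form serves as a predictor.
2. Because either model assumes data missing at random, add a tipping-point analysis with separate shifts for non-responders in each arm, covering about 4 to 11 points. Keep the respondents-only t-test as a sensitivity analysis.
3. Send the PPE-15 and VAS to both arms by the same e-mail link with the same reminders, outside JointCOACH, and report response by arm and visit.
4. In Section 4.3, state whether the 10% is relative or absolute, so that the tipping-point result can be judged against a defined target.

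The cost is some SAP wording, slightly more analysis work and one common survey link. The e-mail requirement in Section 4.2 already makes that link feasible.

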## **4. Methods**

### **4.1 Study Design**

The study design is a prospective, randomized trial in which patients undergoing elective primary hip or knee arthroplasty will be offered perioperative use of JointCOACH vs standard of care. A total of 400 patients will be enrolled (200 in each group). The following outcome measures will be collected at the intervals specified in the Schedule of Events:

- Demographics (Age, gender, BMI)
- Comorbidities (Age-Adjusted Charlson Comorbidity Index)
- Surgical details (ASA (or other comorbidity index), Length of surgery (incision to closure), procedure type, operative limb, surgeon)
- Length of hospital stay and discharge disposition
- Number of ED visits and follow-up visits within 90 days
- Number of phone calls and on-call pages within 90 days
- Readmissions and reoperations within 90 days
- Patient satisfaction (VAS satisfaction and PPE-15)
- Provider satisfaction (5-point Likert scale)

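### The primary PPE-15 comparison is a valid but unadjusted t-test; a prespecified adjusted model using data already collected would be a cheap, modest gain in efficiency.

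*Combined protocol and SAP*

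**What the plan says.** Section 4.5 (Data Analysis Plan) gives one primary test: "A superiority hypothesis test using the two-independent sample t-test will be used to statistically evaluate" the between-arm difference in average satisfaction. It names no covariate, no stratification factor and no adjusted sensitivity analysis.

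Section 4.1 (Study Design) lists demographics, the age-adjusted Charlson index and surgical details that include "procedure type, operative limb, surgeon". Section 4.2 lists ten surgeons grouped under four hospitals. Hospital is not itself a listed variable, but it follows from surgeon if each surgeon operates at one hospital. Section 4.4 (Schedule of Events) marks "HOOS Jr / KOOS Jr" and Promise 10 preoperatively. PPE-15 is scheduled only after surgery.

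Section 4.1 describes the trial as randomised and mentions no stratification.

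**The concern.** PPE-15 measures experience of care. Surgeon, hospital and type of joint are plausible sources of variation in it, and so are comorbidity and health before surgery. An unadjusted test leaves whatever variance these factors explain in the error term. If they predict the outcome, the confidence interval is wider than the collected data require, and a chance imbalance between arms on a predictive factor goes straight into the estimate.

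Timing matters too. Covariates named before the results are seen are uncontroversial. Covariates added afterwards invite the suspicion that they were chosen for their effect on the p-value.

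**Working it through.** **Inputs from section 4.3.** Control mean 24.7%; spread 7.7; a 10% difference; alpha 0.05; power 80%; 153 per group. Sidedness is not stated. The spread is given only as a plus/minus value and is taken here as a between-patient SD.

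**Reproducing the plan's figure.** Read the 10% as relative: δ = 0.10 × 24.7 = 2.47 points. Then

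n per group = 2(z₀.₉₇₅ + z₀.₈₀)²σ²/δ² = 2 × (1.960 + 0.842)² × 7.7² / 2.47² = 152.6, so 153.

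This matches, so the sample size also assumes no adjustment. Other readings fail: one-sided gives 121, and an absolute 10 points two-sided gives 10.

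**Unadjusted power.** SE = 7.7 × √(2/153) = 0.880 and δ/SE = 2.81. Power is 79.9% by the noncentral t distribution on 304 degrees of freedom (80.1% by the normal approximation).

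**Adjusted power, net of fitting cost.** Let R² be the share of outcome variance explained by k covariate terms, with N = 306 analysed. Then

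SE = 7.7 × √(1 − R²) × √(2/153) × √[(N − 3)/(N − 3 − k)], with N − 2 − k degrees of freedom.

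The variance inflation from fitting is 303/299 = 1.013 for 4 terms, 303/295 = 1.027 for 8, and 303/290 = 1.045 for 13.

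Counting terms:
- Procedure (1), hospital (3) and Charlson index (1) make 5. Two preoperative scores bring this to 7, so 8 leaves one spare.
- The 4-term case is procedure, Charlson index and the two scores.
- The 13-term case adds nine fixed surgeon terms to those four.

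R² is not in the documents. The range below is assumed and starts at zero.

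| R² | Fitting cost ignored | 4 terms | 8 terms | 13 terms |
|---|---|---|---|---|
| 0 | 80% | 79% | 79% | 78% |
| 0.05 | 82% | 81% | 81% | 80% |
| 0.10 | 84% | 83% | 83% | 82% |
| 0.20 | 88% | 87% | 87% | 86% |

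**Break-even.** Setting (1 − R²)(N − 3)/(N − 3 − k) = 1 gives R² = k/(N − 3): 4/303 = 1.3%, 8/303 = 2.6%, 13/303 = 4.3%.

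**Worst case.** If the covariates explain nothing, power falls from 79.9% to 78.8% with 8 terms and to 78.1% with 13. Both losses are under 2 points.

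**Dependence on the SD.** The relative gain in information, 1/(1 − R²) before fitting cost, does not involve the SD: 1.05, 1.11 and 1.25 at R² of 0.05, 0.10 and 0.20. The absolute power figures do. If the between-patient SD were 15 to 25 (assumption), unadjusted power for 2.47 points at 153 per group would be about 30% to 14%. R² = 0.20 would raise it only to about 36% to 16%, even with fitting cost ignored.

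**The case against.** The strongest reply is that nothing here is wrong. A two-sample t-test is valid in a simply randomised trial, its error rate already allows for chance imbalance, and the documents describe no stratified randomisation that would call for adjustment. That stands. A reader might infer that the primary test is biased or invalid, and the documents do not support that.

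A reader might also infer that precision is being thrown away for nothing, with power of 84%, 88% or 92% on offer at R² of 10%, 20% or 30%. The documents do not support this either:
- No covariate correlation with PPE-15 is given, and the usual strong covariate, the outcome's own baseline, does not exist. Low values of R² are therefore as admissible as high ones.
- Those figures leave out the cost of fitting. With nine fixed surgeon terms the model loses power if R² is below about 4%.
- Section 4.3 ties the spread to "7.7) for the percent of respondents across all PPE-15 domains", which does not establish a between-patient SD. If the true SD is much larger, adjustment is a minor matter beside the definition of the endpoint.

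The preoperative scores need particular care. Section 1 says that JointCOACH runs from the scheduling of surgery and distributes surveys. The timing of randomisation is not stated, and these scores are absent from the list of measures in section 4.1. A preoperative score could therefore be taken after exposure begins, or be collected less completely in controls. Adjusting for it unconditionally could introduce a problem that the t-test does not have.

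What survives is that procedure, surgeon and Charlson index do not depend on that timing, and that the possible loss is small and bounded.

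**Conclusion.** The point holds as a cheap improvement. The planned test is valid, and the adjusted model is likely to be somewhat more efficient if the covariates explain more than about 2.6% of the variance with 8 terms. Over an assumed R² of 0 to 0.20, net power is 79% to 87%, against 80% unadjusted. The gain is about 1 point at R² = 0.05 and about 3 points at 0.10.

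These figures rest on three assumptions that the documents do not settle: the R² range, the relative reading of the 10% difference, and 7.7 as a between-patient SD. The direction of the argument and the break-even values do not depend on the last two.

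**What to change.** Replace the test in section 4.5 with a prespecified linear model, to be fixed before any comparison by arm is seen:

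- **Outcome:** each patient's PPE-15 problem score, defined as the share of domains in which that patient reports a problem. When all domains are answered, its arm mean equals the quantity that section 4.5 already defines. Name the time point.
- **Covariates:** arm, procedure (hip or knee), hospital derived from surgeon (or surgeon as a random effect), and age-adjusted Charlson index. Age needs no separate term because the index already includes it.
- **Conditional covariates:** preoperative HOOS Jr/KOOS Jr, standardised within procedure because the instrument differs by joint, and Promise 10. Include them only if they are confirmed as collected before randomisation in both arms.
- **Inference:** robust standard errors, a stated rule for missing covariates, and the unadjusted t-test kept as a sensitivity analysis.

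The cost is one paragraph in section 4.5, a check on when the scores are taken, and the missing-covariate rule. No added visits or patients are needed. The downside is a loss of under 2 power points if the covariates explain nothing.
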